- Output (in ml) and characteristics of the perihepatic drains (drain pigmentation, i.e. biliary bloody clear), if the drainage is still in place
- Timing of abdominal drainage removal, if applicable
- · Concomitant medications recordings
- · Adverse Event assessment and recording

Visit 8 (6-8 weeks after Surgery): End of Study Visit

- Hematology examinations, which includes: glucose, urea nitrogen, creatinine, sodium, potassium, calcium, total cholesterol, HDL and LDL, triglyceride, alkaline phosphatase, LDH, complete blood cell counts with differential and platelet counts, APTT, PT, INR, fibrinogen, VES, PCR
- Liver function test examinations, which include: ALT, AST, ALP, bilirubin and total protein, gamma-GT.
- Output (in ml) and characteristics of the perihepatic drains (drain pigmentation, i.e. biliary bloody clear), if the drainage is still in place
- Concomitant medications recordings
- · Adverse Event assessment and recording

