6.2 Exclusion criteria

- 1. Trauma surgery
- 2. Active sepsis around the liver
- 3. Documented history of cirrosis
- 4. Pregnant or nursing women
- 5. Severe coagulopathy (defined as an International normalized ratio INR >2.0)
- 6. Severe Liver disfunction, as per clinical assessment
- 7. Previous liver transplantation
- 8. Laparoscopic procedure
- 9. Any other intraoperative finding, which defines the non eligibility of the patient for liver resection
- 10. Known hypersensitivity to bovine proteins or brilliant blue
- 11. Mental condition rendering the patient unable to understand the nature, scope and possible consequences of the study

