11.2 Analysis populations

For this study, two populations will be considered:

Safety population defined as all patients who signed the Informed Consent. This population will be used for the safety and tolerability analyses.

Intention-To-Treat (ITT) population defined as all the randomized patients who received the assigned treatment. This population will be used for the efficacy analyses.

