11.3 Methods

The analyses will be performed with SAS version 9.4. All the variables will be descriptively analyzed by treatment and visit (mean, median, standard deviation, minimum and maximum for continuous variables, frequency distribution for categorical variables).

All the analyses to be carried out will be detailed in the Statistical Analysis Plan (SAP) which will be finalized in Version 1.0 before the Data Base freezing. Version 2.0 of the SAP will be prepared after the Data Review Meeting (in which the protocol violations will be evaluated) and will include the list of the patients belonging to the defined populations and the randomization list.

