11.6 Safety analyses

The Safety population will be used to evaluate safety and tolerability data.

Physical examinations, vital signs, laboratory tests, adverse events and concomitant medications will be considered for the safety and tolerability evaluation.

Categorical variables (physical examination normality, etc.) will be analyzed with shift tables (baseline vs. last visit), while continuous variables (laboratory parameters, vital signs, etc.) by descriptive summaries.

Laboratory data will also be analysed with shift tables (baseline vs. last visit), considering each value as being normal/abnormal with respect to the appropriate normal ranges.

Baseline conditions and adverse events will be coded using the MedDRA dictionary. All the data related to the baseline conditions and adverse events will be listed by patient. Descriptive statistics will be performed classifying the events by system organ class and preferred term; they will also be classified by seriousness and relationship with the study treatment.

Prior and concomitant medications will be summarized using the WHO coding system.

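### Two-level normal/abnormal coding in the Section 11.6 laboratory shift tables leaves no cell for worsening in patients who enter abnormal

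*Protocol*

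**What the plan says.** Protocol Section 11.6 gives laboratory data two treatments. Values are summarised as "continuous variables (laboratory parameters, vital signs, etc.) by descriptive summaries"; Section 11.3 specifies these as "mean, median, standard deviation, minimum and maximum for continuous variables", by treatment and visit. In addition there are shift tables from baseline to last visit, "considering each value as being normal/abnormal with respect to the appropriate normal ranges". No direction (low or high) and no degree of abnormality is mentioned.

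Entry does not require normal values. Section 6.2 excludes "Severe coagulopathy (defined as an International normalized ratio INR >2.0", and "Severe Liver disfunction, as per clinical assessment" with no numeric limit. Documented cirrhosis is also excluded.

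The tests concerned are repeated. The blood panel at screening and at Visit 8 (Section 5.2) includes "platelet counts, APTT, PT, INR, fibrinogen, VES, PCR", and the liver tests are taken at both visits.

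Three other provisions bear on the point:

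- Section 11.6 lists adverse events by patient and summarises them: "Descriptive statistics will be performed classifying the events by system organ class and preferred term".
- Section 6.3 makes the occurrence of an exclusion-criterion situation during the study a ground for discontinuation.
- Section 11.2 bases safety analyses on a population "defined as all patients who signed the Informed Consent".

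**The concern.** A shift table is there to show how each patient's status moved from baseline. Coded in two levels, it can do so in the adverse direction only for patients who start normal. This trial enrols patients having liver resection, including for hepatocellular, hilar and biliary carcinoma, so some abnormal liver or coagulation values at entry are plausible, although the protocol gives no frequency. For those patients, a marked deterioration and a stable value fall in the same cell.

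At stake is the count, by arm, of patients whose laboratory status got worse. For INR the protocol has already named a level that matters, 2.0, and the table cannot show who crossed it from an abnormal start.

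**Working it through.** The plan gives no figure on this point to reproduce, and the sample size has no bearing on it. The check is on the structure of the table, followed by a small constructed example.

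**Inputs.** Two-level code and baseline-to-last-visit comparison: Section 11.6. INR up to and including 2.0 eligible: Section 6.2. Continuous statistics: Section 11.3. Assumption: the upper limit of normal (ULN) for INR is not in the protocol. Values from the ULN to 2.0 are both abnormal and eligible for any ULN below 2.0.

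**Step 1: cells.** A two-level table has four:

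| Baseline | Last visit | Reads as |
|---|---|---|
| normal | normal | unchanged |
| normal | abnormal | worse |
| abnormal | normal | improved |
| abnormal | abnormal | unchanged |

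From an abnormal baseline only the last two rows are reachable, and neither records worsening. For a test with a two-sided range, low-to-high and high-to-low both fall in the last row.

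**Step 2: one patient.** INR 1.5 at baseline and 2.5 at last visit is a rise of 2.5 − 1.5 = 1.0, or 1.0/1.5 = 67%. For any ULN below 1.5 it is coded abnormal to abnormal, the same as 1.5 to 1.5. With INR split at 2.0 it moves from high (up to 2.0) to above 2.0.

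**Step 3: do the continuous summaries recover the count?** Take two groups of 7, all entering above range but not above 2.0, with an assumed ULN below 1.3. Last-visit INR:

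- Group 1: 1.3, 1.4, 2.0, 2.0, 2.0, 2.0, 2.5
- Group 2: 1.3, 1.5, 1.7, 2.0, 2.1, 2.1, 2.5

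In both groups the sum is 13.2 and the sum of squares 25.90. Hence:

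- mean = 13.2/7 = 1.886
- SD = √[(25.90 − 13.2²/7)/6] = √(1.0086/6) = 0.410
- median 2.0, minimum 1.3, maximum 2.5

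All five planned statistics agree. The two-level table reads 7 of 7 abnormal to abnormal in each group. Yet 1 of 7 is above 2.0 in group 1 and 3 of 7 in group 2. The maximum of 2.5 does show that at least one patient in each group crossed; what is lost is how many.

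**Step 4: would low/normal/high be enough?** It separates low-to-high moves. It still codes a liver test that goes from high to much higher as high to high. A further high category is needed for those tests.

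**Step 5: who is counted.** Consent precedes the screening blood tests (Section 5.2), so the Safety population includes screen failures, among them anyone excluded for INR above 2.0. A last available INR above 2.0 is therefore not always a new crossing in that population, and the denominator is not simply 49 per arm.

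**The case against.** The case against has four parts.

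- **Detail for the SAP.** Section 11.3 sends all analyses to the SAP, and table categories usually belong there. The SAP may indeed refine the display. But Section 11.6 names the two levels itself, so an SAP that follows the protocol inherits them.
- **Covered elsewhere.** Adverse events are assessed at every visit and listed by patient. An INR above 2.0 arising during the study is an exclusion-criterion situation, hence a discontinuation ground under Section 6.3. The by-visit maximum reveals that a crossing happened. All of this stands as partial cover. However, the protocol does not say which laboratory changes must be reported as adverse events, Section 11 specifies no tabulation of discontinuations by reason, and the maximum does not count patients.
- **The example is constructed.** It is: fourteen chosen values, matched on five statistics. It shows that the count can be lost, not how often it would be.
- **Little gain at the last visit.** For completers that is 6 to 8 weeks after surgery, and earlier transient worsening stays out of the table under either coding. This stands; the by-visit summaries cover that period at group level.

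A reader might infer that laboratory deterioration would go undetected in the trial, or that its safety conclusions are unsound. The documents do not support that: the table is additional to continuous summaries and adverse event reporting, and no primary or secondary endpoint rests on it.

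**Conclusion.** The point holds, and it is minor. As Section 11.6 is written, a patient who enters with an abnormal value can appear in the laboratory shift table only as unchanged or improved, and low-to-high moves are invisible. This follows from the two-level code and the Section 6.2 entry limits; for INR the only assumption is a ULN below 2.0. The number of patients concerned cannot be derived from the protocol, and the exclusion of documented cirrhosis makes the group smaller. The consequence is limited to one supplementary descriptive table, with partial cover from other outputs, none of which is specified to count by arm the patients who worsened. It is worth changing because the change is cheap.

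**What to change.** In Section 11.6:

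- Replace the two levels with low / normal / high.
- Split INR high at the protocol's own 2.0.
- Add a further high category for liver tests, for example at a prespecified multiple of the ULN, so that high-to-higher moves show.
- Report by arm, among randomised patients with both a baseline and a last-visit value, the number who move to a worse category. List low-to-high and high-to-low moves separately.
- Show screen failures separately.

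The cost is a short change of wording in 11.6, carried into the SAP, using data already collected: no new tests, visits or patients. The tables become slightly larger and their cells sparser. Worsening that resolves before the last visit remains unseen in this table.

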12. ETHICAL ISSUES

12.1 Ethical approvals

Before the start of the study, the written information to be provided to the patients and the Informed Consent form must be submitted to the review and approval of the local Ethics Committee of the Fondazione Policlinico Universitario A. Gemelli, together with the protocol.

The Informed Consent must be requested, obtained and documented by the Principal Investigator in accordance with applicable legislation, with the Good Clinical Practice and with the ethical principles which derive from the Declaration of Helsinki and subsequent revisions (Appendix II).

12.2 Amendments to the protocol

An amendment can be substantial and non-substantial. A substantial amendment is defined as an amendment to the terms of the application, or to the protocol or any other supporting documentation, that is likely to affect to a significant degree:

- √ the safety or physical or mental integrity of the subjects of the study;
- √ the scientific value of the study;
- √ the conduct or management of the study; or
- ✓ the quality or safety of any investigational medicinal product used in the trial.

The substantial amendments should be submitted in order to make visible changes. To this end, the Principal Investigator must submit both a version with tracked changes and a version clean. The version clean must have a new numbering and dated. A copy of the previous version must be archived.

Substantial amendments must be submitted to the evaluation of the local Ethics Committee and notified to the Regulatory Authority. Only if the local Ethics Committee has not expressed objections, the amendment can be applied. Non-substantial amendments are changes to the detail of the study which do not have a significant impact either on the subjects enrolled in the trial or the conduct, management or scientific value of the trial. Non-substantial amendments must only be notified to the local Ethics Committee.

12.3 Informed Consent

The Principal Investigator and/or his delegates must explain to each patient the nature of the study, its purpose, the procedures involved, the expected duration, the potential risks and benefits involved and any discomfort it may entail. Each patient must be informed that participation in the study is voluntary and that he/she may withdraw from the study at any time and that withdrawal of consent will not affect her subsequent medical treatment or relationship with physician. The informed consent will be given by means of standard written statement, written in non-technical language. The patient should read and consider the statement before signing and dating it, and should be given a copy of the signed document. No patient can enter the study before his informed consent has been obtained. Confirmation that the Informed Consent was obtained will also be documented in the patient's medical record and in the eCRF. If a protocol amendment is made and also the Informed Consent may need to be revised, after the Ethics Committee has

approved changes, it is responsibility of the PI and/or his delegates to inform all active patients affected by changes, and to receive their written and dated "new" Informed Consent for continuation in the study.

13. ADMINISTRATIVE PROCEDURES

13.1 Possible changes in the clinical trial or in the analysis planned

Once the protocol is signed by the Principal Investigator, approved by the local Ethics Committee and notified to the Regulatory Authority, the protocol cannot be modified. Any change made to the protocol must be approved by local Ethics Committee after presenting an amendment and notified to the Regulatory Authority.

13.2 Archiving of study records

Essential documents should be retained for a minimum of 7 years after the end of the study. However, documents should be retained for a longer period if required by the terms of the clinical trial authorization.

13.3 Use of the information and publication of the results

The Principal investigator and his study staff involved in the clinical study are responsible for publishing the results of the study and for their sharing with the Regulatory Authority/ies.

13.4 Insurance coverage and civil liability

The Sponsor has activated an insurance coverage for the trial, as per GCP and local laws pertaining the management of clinical trials requirements.

14. PRINCIPAL INVESTIGATOR RESPONSIBILITIES

[figure not shown]
The Principal Investigator is aware of his responsibility for all the actions delegated by him to other members of his study staff assigned to the conduct of the study. The Principal Investigator and his staff are obliged to conduct the study in compliance with the study protocol and in adherence to the Good Clinical Practice and with the principles of the Declaration of Helsinki (1964) and successive revisions (Appendix II) as well as in respect of applicable legislation. Being the study referencing a Medical Device, compliance will be ensured also to applicable sections of the MEDDEV 2.7/3, December 2010, (Guideline on Medical Devices) and MEDDEV 2.12-1, rev 8, January 2013 (Guideline on a Medical Devices Vigilance System).

14.1 Direct access to original documents

The Principal Investigator and/or his delegates must allow the Regulatory Authority/ies and individuals delegated by the Independent Ethics Committee to have free access to and to conduct the relevant verification of all the original documentation of the study, including the informed consent forms signed by the patients enrolled into the study, the relevant patient files and/or out-patient files. Those individuals who are given free access to the documentation must take every reasonable precaution to keep the identity of the patients as reserved information, in accordance with applicable legislation.

15. REPORT OF THE END OF THE STUDY

A final clinical study report will be produced by the Principal Investigator on the basis of the statistical report.

16. APPENDIX

16.1 Appendix I

Segnalazione Iniziale

Form to be used to report incidents and near incidents with the medical device

Follow Up \square

[figure not shown]
Dati Generale sull'Indagine Clinica				
Centro				
Denominazione della struttura				
Protocollo di studio				
Dati relativi al Dispositivo Medic	o			
Fabbricante (nome, ragione				
sociale e indirizzo)				
Fornitore (nome, ragione sociale e indirizzo)				
Nome commerciale ed eventuale modello del dispositivo				
Descrizione del dispositivo medico				
N. codice del dispositivo assegnato dal fabbricante				
Numero di lotto o di serie				
Data di scadenza				
Codice Classificazione unica nazionale dispositivi medici (CND)				
Dispositivo su misura □				
Se Sì, specificare il campo di applicazione, la tipologia e l'origine del materiale				
Sistemi o kit □				
Prodotto sterile Non sterile				
Dispositivo monouso □ pluriuso □				

Dati Relativi All'even	ıto				
L'episodio ha coinvolto:			l'operatore	П	
ID Paziente:			roperatore		
Nel caso di dispositiv	· · · · · · · · · · · · · · · · · · ·				
Data dell'impianto (se con	-	,			
Dati sull'utilizzo del o					
		c)			
Il dispositivo è stato utiliz	zato	Sì I	□ No		
Motivo per il quale è stato utilizzato (o si intendeva utilizzare) il dispositivo; per i dispositivi impiantabili, indicare anche la specifica diagnosi:					
Nel caso di effettivo util paziente, tempo di perma				, clinica, chirurgica, contatto con il	
Descrizione dell'Incidente/Mancato Incidente					

Esito			
Risolto			Data risoluzione:
Risolto con sequelae			Data risoluzione:
Ongoing			
Morte			
Data di morte:			_
L'evento è giudicato	correla	ato al Di	M in sperimentazione?
SI 🗆		NO	
Argomentare il giudi	zio di c	orrelazi	ione
Il DM ("specifico pezzo")	coinvolt	o à dispo	nihila
ii Divi (specifico pezzo)	Sì		mblie:
	No		
Se sì, dove:			
A *****			
Azioni intraprese			

Ulteriori commenti e dettagli

Dati del segnalatore		
Dati dei segnalatore		
Nome e cognome:		
Firma:	Data:	
Data di avvenuta conoscenza da parte del Segnalatore:		
Data di avvenuta conoscenza d	a parte dei Segnalatore:	

16.2 APPENDIX II Declaration of Helsinki

Adopted by the 18th WMA General Assembly, Helsinki, Finland, June 1964
and amended by the:

29th WMA General Assembly, Tokyo, Japan, October 1975
35th WMA General Assembly, Venice, Italy, October 1983
41st WMA General Assembly, Hong Kong, September 1989
48th WMA General Assembly, Somerset West, Republic of South Africa, October 1996
52nd WMA General Assembly, Edinburgh, Scotland, October 2000
53rd WMA General Assembly, Washington DC, USA, October 2002 (Note of Clarification added)
55th WMA General Assembly, Tokyo, Japan, October 2004 (Note of Clarification added)
59th WMA General Assembly, Seoul, Republic of Korea, October 2008
64th WMA General Assembly, Fortaleza, Brazil, October 2013

Preamble

1. The World Medical Association (WMA) has developed the Declaration of Helsinki as a statement of ethical principles for medical research involving human subjects, including research on identifiable human material and data.

The Declaration is intended to be read as a whole and each of its constituent paragraphs should be applied with consideration of all other relevant paragraphs.

2. Consistent with the mandate of the WMA, the Declaration is addressed primarily to physicians. The WMA encourages others who are involved in medical research involving human subjects to adopt these principles.

General Principles

- **3.** The Declaration of Geneva of the WMA binds the physician with the words, "The health of my patient will be my first consideration," and the International Code of Medical Ethics declares that, "A physician shall act in the patient's best interest when providing medical care."
- **4.** It is the duty of the physician to promote and safeguard the health, well-being and rights of patients, including those who are involved in medical research. The physician's knowledge and conscience are dedicated to the fulfilment of this duty.
- 5. Medical progress is based on research that ultimately must include studies involving human subjects.
- **6.** The primary purpose of medical research involving human subjects is to understand the causes, development and effects of diseases and improve preventive, diagnostic and therapeutic interventions (methods, procedures and treatments). Even the best proven interventions must be evaluated continually through research for their safety, effectiveness, efficiency, accessibility and quality.
- **7.** Medical research is subject to ethical standards that promote and ensure respect for all human subjects and protect their health and rights.

- **8.** While the primary purpose of medical research is to generate new knowledge, this goal can never take precedence over the rights and interests of individual research subjects.
- **9.** It is the duty of physicians who are involved in medical research to protect the life, health, dignity, integrity, right to self-determination, privacy, and confidentiality of personal information of research subjects. The responsibility for the protection of research subjects must always rest with the physician or other health care professionals and never with the research subjects, even though they have given consent.
- **10.** Physicians must consider the ethical, legal and regulatory norms and standards for research involving human subjects in their own countries as well as applicable international norms and standards. No national or international ethical, legal or regulatory requirement should reduce or eliminate any of the protections for research subjects set forth in this Declaration.
- 11. Medical research should be conducted in a manner that minimises possible harm to the environment.
- **12.** Medical research involving human subjects must be conducted only by individuals with the appropriate ethics and scientific education, training and qualifications. Research on patients or healthy volunteers requires the supervision of a competent and appropriately qualified physician or other health care professional.
- **13.** Groups that are underrepresented in medical research should be provided appropriate access to participation in research.
- **14.** Physicians who combine medical research with medical care should involve their patients in research only to the extent that this is justified by its potential preventive, diagnostic or therapeutic value and if the physician has good reason to believe that participation in the research study will not adversely affect the health of the patients who serve as research subjects.
- **15.** Appropriate compensation and treatment for subjects who are harmed as a result of participating in research must be ensured.

Risks, Burdens and Benefits

16. In medical practice and in medical research, most interventions involve risks and burdens.

Medical research involving human subjects may only be conducted if the importance of the objective outweighs the risks and burdens to the research subjects.

17. All medical research involving human subjects must be preceded by careful assessment of predictable risks and burdens to the individuals and groups involved in the research in comparison with foreseeable benefits to them and to other individuals or groups affected by the condition under investigation.

Measures to minimise the risks must be implemented. The risks must be continuously monitored, assessed and documented by the researcher.

18. Physicians may not be involved in a research study involving human subjects unless they are confident that the risks have been adequately assessed and can be satisfactorily managed.

When the risks are found to outweigh the potential benefits or when there is conclusive proof of definitive outcomes, physicians must assess whether to continue, modify or immediately stop the study.

Vulnerable Groups and Individuals

19. Some groups and individuals are particularly vulnerable and may have an increased likelihood of being wronged or of incurring additional harm.

All vulnerable groups and individuals should receive specifically considered protection.

20. Medical research with a vulnerable group is only justified if the research is responsive to the health needs or priorities of this group and the research cannot be carried out in a non-vulnerable group. In addition, this group should stand to benefit from the knowledge, practices or interventions that result from the research.

Scientific Requirements and Research Protocols

- **21.** Medical research involving human subjects must conform to generally accepted scientific principles, be based on a thorough knowledge of the scientific literature, other relevant sources of information, and adequate laboratory and, as appropriate, animal experimentation. The welfare of animals used for research must be respected.
- **22.** The design and performance of each research study involving human subjects must be clearly described and justified in a research protocol.

The protocol should contain a statement of the ethical considerations involved and should indicate how the principles in this Declaration have been addressed. The protocol should include information regarding funding, sponsors, institutional affiliations, potential conflicts of interest, incentives for subjects and information regarding provisions for treating and/or compensating subjects who are harmed as a consequence of participation in the research study.

In clinical trials, the protocol must also describe appropriate arrangements for post-trial provisions.

Research Ethics Committees

23. The research protocol must be submitted for consideration, comment, guidance and approval to the concerned research ethics committee before the study begins. This committee must be transparent in its functioning, must be independent of the researcher, the sponsor and any other undue influence and must be duly qualified. It must take into consideration the laws and regulations of the country or countries in which the research is to be performed as well as applicable international norms and standards but these must not be allowed to reduce or eliminate any of the protections for research subjects set forth in this Declaration.

The committee must have the right to monitor ongoing studies. The researcher must provide monitoring information to the committee, especially information about any serious adverse events. No amendment to the protocol may be made without consideration and approval by the committee. After the end of the study, the researchers must submit a final report to the committee containing a summary of the study's findings and conclusions.

Privacy and Confidentiality

24. Every precaution must be taken to protect the privacy of research subjects and the confidentiality of their personal information.

Informed Consent

- **25.** Participation by individuals capable of giving informed consent as subjects in medical research must be voluntary. Although it may be appropriate to consult family members or community leaders, no individual capable of giving informed consent may be enrolled in a research study unless he or she freely agrees.
- **26.** In medical research involving human subjects capable of giving informed consent, each potential subject must be adequately informed of the aims, methods, sources of funding, any possible conflicts of interest, institutional affiliations of the researcher, the anticipated benefits and potential risks of the study and the discomfort it may entail, post-study provisions and any other relevant aspects of the study. The potential subject must be informed of the right to refuse to participate in the study or to withdraw consent to participate at any time without reprisal. Special attention should be given to the specific information needs of individual potential subjects as well as to the methods used to deliver the information.

After ensuring that the potential subject has understood the information, the physician or another appropriately qualified individual must then seek the potential subject's freely-given informed consent, preferably in writing. If the consent cannot be expressed in writing, the non-written consent must be formally documented and witnessed.

All medical research subjects should be given the option of being informed about the general outcome and results of the study.

- **27.** When seeking informed consent for participation in a research study the physician must be particularly cautious if the potential subject is in a dependent relationship with the physician or may consent under duress. In such situations the informed consent must be sought by an appropriately qualified individual who is completely independent of this relationship.
- **28.** For a potential research subject who is incapable of giving informed consent, the physician must seek informed consent from the legally authorised representative. These individuals must not be included in a research study that has no likelihood of benefit for them unless it is intended to promote the health of the group represented by the potential subject, the research cannot instead be performed with persons capable of providing informed consent, and the research entails only minimal risk and minimal burden.
- **29.** When a potential research subject who is deemed incapable of giving informed consent is able to give assent to decisions about participation in research, the physician must seek that assent in addition to the consent of the legally authorised representative. The potential subject's dissent should be respected.
- **30.** Research involving subjects who are physically or mentally incapable of giving consent, for example, unconscious patients, may be done only if the physical or mental condition that prevents giving informed consent is a necessary characteristic of the research group. In such circumstances the physician must seek informed consent from the legally authorised representative. If no such representative is available and if the research cannot be delayed, the study may proceed without informed consent provided that the specific reasons for involving subjects with a condition that renders them unable to give informed consent have been stated in the research protocol and the study has been

approved by a research ethics committee. Consent to remain in the research must be obtained as soon as possible from the subject or a legally authorised representative.

- **31.** The physician must fully inform the patient which aspects of their care are related to the research. The refusal of a patient to participate in a study or the patient's decision to withdraw from the study must never adversely affect the patient-physician relationship.
- **32.** For medical research using identifiable human material or data, such as research on material or data contained in biobanks or similar repositories, physicians must seek informed consent for its collection, storage and/or reuse. There may be exceptional situations where consent would be impossible or impracticable to obtain for such research. In such situations the research may be done only after consideration and approval of a research ethics committee.

Use of Placebo

33. The benefits, risks, burdens and effectiveness of a new intervention must be tested against those of the best proven intervention(s), except in the following circumstances:

Where no proven intervention exists, the use of placebo, or no intervention, is acceptable; or

Where for compelling and scientifically sound methodological reasons the use of any intervention less effective than the best proven one, the use of placebo, or no intervention is necessary to determine the efficacy or safety of an intervention and the patients who receive any intervention less effective than the best proven one, placebo, or no intervention will not be subject to additional risks of serious or irreversible harm as a result of not receiving the best proven intervention.

Extreme care must be taken to avoid abuse of this option.

Post-Trial Provisions

34. In advance of a clinical trial, sponsors, researchers and host country governments should make provisions for post-trial access for all participants who still need an intervention identified as beneficial in the trial. This information must also be disclosed to participants during the informed consent process.

Research Registration and Publication and Dissemination of Results

- **35.** Every research study involving human subjects must be registered in a publicly accessible database before recruitment of the first subject.
- **36.** Researchers, authors, sponsors, editors and publishers all have ethical obligations with regard to the publication and dissemination of the results of research. Researchers have a duty to make publicly available the results of their research on human subjects and are accountable for the completeness and accuracy of their reports. All parties should adhere to accepted guidelines for ethical reporting. Negative and inconclusive as well as positive results must be published or otherwise made publicly available. Sources of funding, institutional affiliations and conflicts of interest must be declared in the publication. Reports of research not in accordance with the principles of this Declaration should not be accepted for publication.

Unproven Interventions in Clinical Practice

37. In the treatment of an individual patient, where proven interventions do not exist or other known interventions have been ineffective, the physician, after seeking expert advice, with informed consent from the patient or a legally authorised representative, may use an unproven intervention if in the physician's judgement it offers hope of saving life, re-establishing health or alleviating suffering. This intervention should subsequently be made the object of research, designed to evaluate its safety and efficacy. In all cases, new information must be recorded and, where appropriate, made publicly available.

